#### **2.4.4 Analyses of safety data**

##### ***General common rules***

All safety analyses will be performed on the safety population as defined in [Section 2.3.2](#), unless otherwise specified, using the following common rules:

- The baseline value for safety parameters is the original baseline from the previous studies.
- The value at Week 0 is the last non~ missing measurement in data collected at scheduled visits: visit1, visit2 and/or visit1/2 in LTS11210 or EOT visit of previous studies prior to first IMP in LTS11210 study design.
- The Potentially Clinically Significant Abnormality (PCSA) values are defined as abnormal values considered medically important by the sponsor according to predefined criteria/thresholds based on literature review and defined by the sponsor for clinical laboratory tests, vital signs and ECG (PCSA version in BTD-009536 version 3, see [Appendix A](#)).
- PCSA criteria will determine which patients had at least one PCSA during the TEAE period, taking into account all evaluations performed during the TEAE period, including non-scheduled or repeated evaluations. The number of all such patients will be the numerator for the on-treatment PCSA percentage.
- The treatment emergent PCSA denominator by group for a given parameter will be based on the number of patients assessed for that given parameter in the TEAE period by treatment received on the safety population.
- For quantitative safety parameters based on central laboratory/reading measurements, descriptive statistics will be used to summarize results and change from baseline values by visit and treatment received. Summaries will include the endpoint value. The endpoint value is commonly defined as the value collected at the same day/time of the last dose of investigational product. If this value is missing, this endpoint value will be the closest one prior to the last dose intake.
- The analysis of the safety variables will be essentially descriptive and no systematic testing is planned.

### **2.4.4.1 Analyses of adverse events**

#### ***Generalities***

The primary focus of adverse event reporting will be on TEAEs. Pre-treatment and post-study AEs will be described separately.

If an AE date/time of onset (occurrence, worsening, or becoming serious) is incomplete, an imputation algorithm will be used to classify the AE as pre-treatment, or TEAE. The algorithm for imputing date/time of onset will be conservative and will classify an AE as a treatment emergent unless there is definitive information to determine it is pre-treatment. Details on classification of AEs with missing or partial onset dates are provided in [Section 2.5.3](#).

Adverse event incidence tables will present by system-organ-class (SOC), High level group term (HLGT), High level term (HLT) and preferred term (PT) sorted in alphabetical order by treatment received and overall, the number (n) and percentage (%) of patients experiencing an AE. Multiple occurrences of the same event in the same patient will be counted only once in the tables within a dose group. Overall counts will also be provided, counting each patient once and also counting the total number of events. The denominator for computation of percentages is the safety population within the treatment group.

The incidence and number of events per 100 patient-years (number of events adjusted for the total duration of exposure) will be provided for all the TEAE summaries. In addition, the number of patients with event(s) per 100 patient-years (number of patients adjusted for the exposure up to the first event or up to the end of the duration of exposure for patients with no event) will also be provided for serious TEAEs and for each type of adverse event of special interest (AESI).

Sorting within tables should ensure same presentation. For that purpose, the table of all TEAEs presented by SOC and PT sorted by internationally agreed order of SOC and decreasing frequency of PT within SOC will define the presentation order for all other tables unless otherwise specified. Sorting will be based on results for overall sarilumab group.

Listings will be provided for all pre-treatment AEs, all TEAEs, all SAEs, all CV events undergone adjudication, and TEAEs leading to treatment discontinuation with flags indicating on-treatment status

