Investigational Medicinal Product(s)  Formulation	
Sarilumab (anti-Interleukin 6R<math>\alpha</math> monoclonal antibody (Anti-IL6R<math>\alpha</math> mAb)
 
Two different pharmaceutical forms are used in the study: C1F2 used in vials and C2F3 (pivotal formulation) used in prefilled syringes.
 
Before Phase 3 pivotal dose selection decision: vials 150 mg (75 mg/ml)
 
After Phase 3 pivotal dose selection decision, and prior to availability of prefilled syringes: vials 150 mg (75 mg/mL), and 200 mg (100 mg/mL)
 
After Phase 3 pivotal dose selection decision, upon availability of prefilled syringes: prefilled syringes filled with 150 mg (131.6 mg/ml) or 200 mg (175 mg/ml) of drug product
 
In the sub-study: prefilled syringes with a needle safety shield (PFS-S) with exactly the same IMP formulation as the PFS used in the main study

Route(s) of administration:	Subcutaneous (SC) injection in the abdomen, thigh, or upper arm Injection volume: 2 mL (vials); 1.14 mL (prefilled syringes)
Dose regimen:	
Before the phase 3 pivotal dose selection decision, the sarilumab dose was 150 mg weekly (qw) (dose reduction to 150 mg q2w in case of neutropenia, thrombocytopenia, or an increase in liver enzymes (ALT).
 
After the phase 3 pivotal doses were selected; the sarilumab dose is 200 mg q2w and the reduced dose is 150 mg q2w.
 
Note: Patients enrolled in the study prior to the dose selection decision and receiving 150 mg qw were switched to 200 mg q2w. Patients who prior to the dose selection decision were assigned to the step-down dose of 150 mg q2w because of a safety issue continued to receive sarilumab 150 mg q2w.

Noninvestigational Medicinal Products (except EFC13752 patients)	
One or a combination of non-biologic disease modifying drugs (DMARDs).
 
Folic/Folinic acid in patients using MTX.
 
Formulation, route of administration and dose regimen should follow the applicable local labeling information.

PRIMARY AND SECONDARY ENDPOINT(S)	
Primary endpoint: Safety assessment of sarilumab over time.
 
Secondary Endpoint(s):
 
 
• The proportion of patients who achieve American College of Rheumatology criteria ACR20/ACR50/ACR70, DAS28 (Disease activity score) Remission, and EULAR (European League against Rheumatism) Response over time.
 
• DAS28-CRP over time
 

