## 4 INTRODUCTION AND RATIONALE

Rheumatoid arthritis (RA) is a chronic, debilitating disease that primarily affects the synovial membrane of diarthrodial joints.

Currently, treatment of RA involves the use of nonsteroidal anti-inflammatory drugs (NSAIDs), glucocorticoids and disease modifying anti-rheumatic drugs (DMARDs). Methotrexate, sulfasalazine, hydroxychloroquine and leflunomide are DMARDs that have been used by rheumatologists for many years (1)(2)(3).

Introduction of biologic agents, especially inhibitors of TNF- $\alpha$ , has greatly improved the therapeutic options available for treating RA (4)(5)(6)(7)(8)(9); however, no therapeutic modality provides either universal or complete control of disease and safety remains one of the key issues with anti-TNF- $\alpha$  treatment (10)(11).

Besides early benefit/risk of biologics, the long term outcome of RA remain a critical question: long term use of biologics have been associated with immunosuppression and effects on the development of infections, malignancies, demyelinating events, lupus like events, etc. Consequently, long-term data are needed to investigate the risks associated with the long-term use of these drugs.

This LTS11210 study is intended to identify potential late onset adverse events associated with long-term use of sarilumab with or without concomitant non-biologic DMARD(s), including MTX, as well as to assess long-term efficacy.

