### **2.1.3 Safety endpoints**

The primary endpoint is the incidence of adverse events. The safety analysis will be based on the reported adverse events (AEs) and other safety information, such as clinical laboratory data, vital signs and ECG.

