#### ***Analysis of adverse events of special interest (AESI)***

Summaries of AESI defined by the search criteria:

- All treatment emergent AESIs, by AESI category and PT, showing number (%) of patients, sorted by decreasing incidence of PT within each AESI category.

- Within each treatment emergent AESI category, at a minimum the data display will include:
  - Overview summary
  - Treatment duration summary
  - Incidence by patient and by event
  - Serious TEAEs
  - TEAEs leading to treatment discontinuation
  - TEAEs leading to death
  - Possibly related TEAEs

The number at risk and the number with events will be provided by visit and treatment group

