#### ***Analysis of adjudicated CV events***

The following CV event summaries will be generated for the safety population:

- MACE (primary) and MACE (narrow), showing number (%) of patients with at least one adjudicated treatment-emergent CV event and number of such events per 100 patient-years (number of events adjusted for the total duration of exposure).
- All adjudicated treatment-emergent CV events by CV events categories, showing number (%) of patients with at least one adjudicated treatment-emergent CV event and number of events per 100 patient-years, sorted by alphabetical order.
- All events undergone adjudication, all events adjudicated as non-CV event, and all events that are not evaluable, showing number (%) of events (patients).

Summary describing the investigator-reported treatment-emergent SAE and the associated CAC adjudication classification will be provided.

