### ***Number of TEAE per 100 patient years***

The number of TEAE per 100 patient years is defined as the total number of TEAEs divided by the total exposure (expressed under the unit of 100 patient years) of the corresponding treatment group. Specifically, it is calculated as follows for each treatment group:

$$\text{Number of TEAE/100 patient years} = (\text{Total number of TEAEs}) / \text{total treatment duration (Unit: 100 patient years)}$$

The total treatment duration is defined as [(end of TEAE period) – (date of first IMP) + 1], where the end of TEAE period is defined as minimum [(the last IMP + 60 days), (last contact date), (death date)], where the last contact date is defined as maximum [last complete AE start date, last visit date, last subject vital status date].

The number of PCSA per 100 patient years for the laboratory values, vital signs and ECGs will be defined similarly.

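### Overall TEAEs, SAEs, deaths and adjudicated MACE are reported only as percentages and rates pooled over all exposure, so they cannot show a change in risk with time on sarilumab

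*SAP*

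**What the plan says.** Protocol section 4 says that the study is "intended to identify potential late onset adverse events associated with long-term use of sarilumab". Treatment lasts at least 264 and at most 516 weeks, except in the UK, where it is 264 weeks (protocol 6.2, SAP 1.1). The protocol synopsis words the primary endpoint as "Safety assessment of sarilumab over time". Protocol 9.1.1 and SAP 2.1.3 are narrower; in the SAP, "The primary endpoint is the incidence of adverse events".

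For the four outcomes at issue the SAP plans:

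- **TEAEs (2.4.4.1, 2.5.1):** n (%) and an event rate. SAP 2.4.4.1 says that the "number of events per 100 patient-years (number of events adjusted for the total duration of exposure) will be provided for all the TEAE summaries", and SAP 2.5.1 defines the rate as "the total number of TEAEs divided by the total exposure (expressed under the unit of 100 patient years) of the corresponding treatment group".
- **SAEs (2.4.4.1, 2.5.1):** the same, plus patients with a first event divided by person-time to first event.
- **Adjudicated MACE (2.4.4.1):** n (%) and events per 100 patient-years of total exposure.
- **Deaths (2.4.4.2):** incidence and a rate over total exposure, with a split into on-treatment, follow-up and post-study. That split is defined by the last dose, not by time since starting drug.

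Rates are given by previous treatment and overall, separately for combination therapy and monotherapy (SAP section 2). SAP Appendix B lists exposure adjustment as the only supportive analysis of adverse events.

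Time-resolved safety displays exist elsewhere in the SAP. For AESIs, "The number at risk and the number with events will be provided by visit and treatment group". Grade 3–4 neutropenia and platelets below 100 Giga/L get Kaplan-Meier onset (2.4.4.3). Laboratory, vital-sign and ECG data are summarised by visit. Liver abnormalities may be shown by duration of exposure.

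**The concern.** A late-onset question asks whether the event rate in years 4 and 5 differs from that in years 1 and 2. A ratio of all events to all person-time cannot answer it, because different time courses can give the same ratio. Splitting by previous treatment does not help: each group's rate is still pooled over time.

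The omission does not reflect a general policy of the plan. Efficacy, the secondary objective, gets yearly summaries (SAP 2.4.5), and exposure is tabulated in intervals, at 24-week steps in the later years (SAP 2.4.3.1). MACE is the sharpest case. Protocol 10.2.10 says that the cardiovascular effect of the lipid elevations is unknown, yet MACE is not an AESI category in SAP Table 1 and so does not receive the by-visit display.

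The clock is a related point. SAP person-time starts at the first LTS11210 dose, while patients arrive after 2 to 52 weeks on sarilumab, placebo or comparator (protocol synopsis and 4.1.2), some EFC11072 patients with sarilumab rescue (SAP 1.1). Time in the extension is therefore not the same as time on drug.

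**Working it through.** **Number of patients.** SAP 1.3: 243 + 1040 + 7 + 168 + 454 + 111 = 2023. SAP 1.1 gives 456 rather than 454 for EFC10832, so 1283 + 7 + 456 + 168 + 111 = 2025. Both agree with the stated figure of approximately 2000. The plan gives no event rate, dropout rate or power figure to reproduce, so all rates and losses below are assumptions.

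**Check 1: can the SAP formula separate different time courses?** Take five years and 10% yearly dropout. Patients starting year k: 2023 × 0.9^(k−1). Patient-years in year k: that number × 0.95, giving 1922, 1730, 1557, 1401 and 1261, in total 7,870 before rounding. Apply total events ÷ total patient-years to three linear time courses, each scaled to the same pooled rate:

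| Time course | Rate per 100 PY, years 1 to 5 | Events | Pooled rate | Years 4–5 ÷ years 1–2 |
|---|---|---|---|---|
| Constant | 9.0 throughout | 708 | 9.0 | 1.00 |
| Doubling | 6.2, 7.8, 9.3, 10.9, 12.4 | 708 | 9.0 | 1.67 |
| Tripling | 4.8, 7.1, 9.5, 11.9, 14.3 | 708 | 9.0 | 2.21 |

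For the doubling row, yearly events are 119.5 + 134.4 + 145.2 + 152.4 + 156.8 = 708.3, and 708.3 ÷ 7,870 = 9.0 per 100 patient-years, with a 95% CI of about ±0.66. The interval is tight and identical in all three rows. With dropout of 5% to 20% a year, the same construction again gives 9.0 in every row, the ratios stay near 1.67 and 2.2, and years 4–5 supply from 37% down to 27% of the exposure.

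**Check 2: a rare event.** Assume a constant loss hazard h of 0.12 a year, 30% of patients continuing past year 5, follow-up to year 7, and a rate of 0.2 per 100 patient-years in years 1–3 and 0.8 afterwards. Patient-years in year k are 2023 × (1 − e^(−h))/h × e^(−h(k−1)), multiplied by 0.3 after year 5: 1906, 1691, 1500, 1330, 1180, 314, 278, in total 8,199.

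- Years 1–3: 5,097 patient-years, about 10 events, rate 0.20 (exact 95% CI 0.09 to 0.36).
- Later: 3,102 patient-years, about 25 events, rate 0.81 (0.52 to 1.19).
- Pooled: (5,097 × 0.2 + 3,102 × 0.8) ÷ 8,199 = 0.43 (0.30 to 0.59).

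The two interval CIs do not overlap; the pooled figure gives no hint of the four-fold rise. For h from 0.05 to 0.20 the pooled rate runs from 0.46 to 0.40.

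**Check 3: limits of interval rates.** For an outcome with a pooled rate of 0.5 per 100 patient-years (31 to 45 events over five years at 5% to 20% dropout), a two-period Wald comparison of log rates, with standard error √(1/e₁ + 1/e₂), has about 24–32% power for a doubling and 50–61% for a tripling.

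**The case against.** The strongest reply is that the late risks named in protocol section 4 (infections, malignancies, demyelinating and lupus-like events) are all AESI categories in SAP Table 1. Each has a by-visit display and, within category, summaries of serious and fatal events. This stands. A reader might infer that the study cannot answer its own late-onset question; the documents do not support that. Nor would it be right to call the AESI display bare counts, because the number at risk is planned beside the number with events.

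Second, a reader might infer that the pooled rate assumes a constant hazard and is therefore invalid. It is a legitimate descriptive average without that assumption, and no systematic testing is planned (SAP 2.4.4). Its weakness is only that it is silent on trend.

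Third, a reader might infer that the plan fails its primary endpoint because that endpoint is safety over time. Only the synopsis uses that wording. The point rests on the late-onset aim in section 4.

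Fourth, listings of all SAEs, deaths and adjudicated CV events would let a reader notice a late cluster. They would, but without person-time at risk a listing cannot separate a rising rate from continued follow-up.

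Fifth, placebo and active-control roll-overs are shown as their own groups, and for most of them LTS11210 entry is the first sarilumab exposure, apart from those given rescue in EFC11072. Prior exposure is at most 52 weeks against at least 264 planned. This largely stands, so the alternative clock is a sensitivity display and not the correction of a defect.

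**Conclusion.** The point holds for overall TEAEs, SAEs, deaths and adjudicated MACE. The plan specifies no interval rate, cumulative-incidence curve or by-visit count for any of them. It does not extend to AESIs, neutropenia or platelets.

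The size can only be illustrated. In the example, a pooled 9.0 per 100 patient-years is compatible with no trend, a doubling or a tripling, and a pooled 0.43 can conceal a rise from 0.2 to 0.8. These figures depend on assumed rates and attrition. That a pooled ratio cannot identify a trend does not depend on them.

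This is an inexpensive improvement that should be made. It is not a flaw that undermines the study, and the data to remedy it are already being collected.

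**What to change.** In SAP 2.4.4.1 and 2.4.4.2, add event rates per 100 patient-years with 95% CIs by 48-week interval, or by the exposure categories already defined in 2.4.3.1, for TEAEs, SAEs, adjudicated MACE and deaths. Present them for the overall sarilumab + DMARD group and the overall monotherapy group. Use person-years accrued within each interval and show patients at risk at its start. For serious infections and malignancy, add interval person-year rates to the AESI by-visit display.

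As a sensitivity display, repeat with time counted from the first sarilumab dose in any study, using the parent-study databases that SAP 2.1.1 already draws on.

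The cost is a few tables and their programming, with no new data. The limits should be stated in the SAP:

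- Late intervals will be sparse and imprecise for rare events.
- Loss of susceptible patients can lower late rates in an uncontrolled study.
- The early switch from 150 mg weekly to 200 mg every two weeks changes the regimen within early follow-up for some patients.
- After week 264, treatment continues only where sarilumab is not yet commercially available, so the mix of countries shifts.

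The display should therefore be labelled descriptive.

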#### ***Analysis of all TEAE(s)***

The following TEAE summaries will be generated for the safety population.

- Overview of TEAEs, summarizing number (%) of patients with any
  - TEAE
  - Serious TEAE
  - TEAE leading to death
  - TEAE leading to permanent treatment discontinuation

- All TEAEs by primary SOC, HLGT, HLT, and PT, showing number (%) of patients with at least one TEAE sorted by SOC internationally agreed order. The other level (HLGT, HLT, and PT) will be presented in an alphabetic order.
- All TEAEs by primary SOC and PT, showing number (%) of patients with at least one TEAE, sorted by SOC internationally agreed order and decreasing incidence of PTs within SOC.
- All TEAEs by relationship, presented by primary SOC, HLGT, HLT and PT, showing number (%) of patients with at least one TEAE, sorted by SOC internationally agreed order. The other level (HLGT, HLT, PT) will be presented in an alphabetic order.
- All TEAEs by maximal severity, presented by primary SOC and PT, showing number (%) of patients with at least one TEAE by severity (i.e., mild, moderate, or severe), sorted by sorting order defined above.

#### ***Analysis of all treatment emergent SAE(s)***

- All treatment emergent SAEs by primary SOC, HLGT, HLT and PT, showing number (%) of patients with at least one serious TEAE, sorted by SOC internationally agreed order. The other level (HLGT, HLT, PT) will be presented in an alphabetic order.
- All treatment emergent SAEs by primary SOC and PT, showing number (%) of patients with at least one TEAE, sorted by SOC internationally agreed order and decreasing incidence of PTs within SOC
- A separate listing of non-treatment emergent SAEs occurred in previous studies which are ongoing from the previous studies into LTS11210 study will be provided.

#### ***Analysis of all TEAE(s) leading to treatment discontinuation***

- All TEAEs leading to treatment discontinuation, by primary SOC, HLGT, HLT and PT, showing number (%) of patients sorted by SOC internationally agreed order. The other level (HLGT, HLT, PT) will be presented in an alphabetic order. The table summary will be presented only if the number of patients concerned is greater than 3.
- All TEAEs leading to treatment discontinuation, by primary SOC and PT, showing number (%) of patients with at least one TEAE, sorted by SOC internationally agreed order and decreasing incidence of PTs within SOC
- A separate listing of AEs (occurred in previous studies) leading to treatment discontinuation in LTS11210, which are ongoing from the previous studies into LTS11210 study, will be provided.

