**Exclusion criteria related to the Sanofi compound:**

- E 03. Any patient who experienced an adverse event leading to permanent discontinuation from a prior study.

E 04. Deleted

E 05. Deleted

E 06. Pregnant or breast-feeding women.

- E 07. Women of childbearing potential (WOCBP) not protected by highly-effective contraceptive method(s) of birth control (as defined in the informed consent form and/or in a local protocol addendum), and/or who are unwilling or unable to be tested for pregnancy.

*(For UK patients: Women of childbearing potential, unwilling to utilize adequate contraception methods or not become pregnant during the full course of the study. Adequate contraceptive measures include:*

- *Placement of an intrauterine device (IUD) or intrauterine system (IUS).*

*Barrier methods of contraception: Condom or Occlusive cap (diaphragm or cervical/vault caps) with spermicidal foam/gel/film/cream/suppository. The use of barrier contraceptives should always be supplemented with the use of a spermicide.*

- *Male sterilisation (with the appropriate post-vasectomy documentation of the absence of sperm in the ejaculate).*
- *True abstinence: When this is in line with the preferred and usual lifestyle of the subject. [Periodic abstinence (e.g., calendar, ovulation, symptothermal, post-ovulation methods) and withdrawal are not acceptable methods of contraception].)*

E 08. Deleted

E 09. Deleted

- E 11. Patients with an abnormality(ies) or adverse event(s) that per investigator judgment would adversely affect patient's safety and/or participation of the patient in the study.

E 13. Patients with temporary IMP discontinuation lasting > 31 days at the time of the planned first dose in the LTS11210 study.

E 14. Patients fulfilling the protocol-defined criteria for the permanent treatment discontinuation.

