### *Adverse events leading to treatment discontinuation*

The number and percentage of patients with adverse events leading to permanent treatment discontinuation will be summarized by primary SOC, HLGT, HLT, and PT.

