#### **2.1.3.1 Adverse events variables**

Adverse event observation period

- Pre-treatment AEs are AEs that developed or worsened or became serious from the signed informed consent date up to first dose of IMP in LTS11210. The ongoing AEs from previous studies filled out on AE switch CRF pages are also considered as pre-treatment AEs

- TEAEs are AEs that developed or worsened or became serious during the TEAE period
- Post-study AEs are AEs that developed or worsened or became serious during the post-study period

All AEs (including SAEs and AESIs and ongoing AEs from previous studies filled out on AE switch CRF pages) will be coded to a “Lowest Level Term (LLT)”, “Preferred Term (PT)”, “High Level term (HLT)”, “High Group Level Term (HLGT)” and associated primary “System Organ Class (SOC)” using the version of MedDRA currently in effect at sanofi at the time of database lock.

The occurrence of AEs (including SAEs and AESIs and ongoing AEs from previous studies filled out on AE switch CRF pages) will be recorded from the time of signed informed consent until the end of the study.

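### SAP 2.4.4.1 leaves an unchanged carried-over AE that ends treatment in LTS11210 out of the AE-discontinuation tables; it appears only in a listing

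*SAP*

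**What the plan says.** SAP 2.1.3.1 defines the classes. An event is treatment-emergent if it developed, worsened or became serious between the first LTS11210 dose and the last dose plus 60 days. Events carried in from a parent study fall elsewhere: "The ongoing AEs from previous studies filled out on AE switch CRF pages are also considered as pre-treatment AEs".

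SAP 2.4.4.1 builds its discontinuation output on that split. The overview has a line for "TEAE leading to permanent treatment discontinuation". The main table is "All TEAEs leading to treatment discontinuation, by primary SOC, HLGT, HLT and PT, showing number (%) of patients sorted by SOC internationally agreed order", and a second table by SOC and PT is also limited to TEAEs. Rates per 100 patient-years are promised for the TEAE summaries. Carried-over events that are still ongoing get a different output: "A separate listing of AEs (occurred in previous studies) leading to treatment discontinuation in LTS11210" is to be provided.

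Protocol 13.5.4.1 words the same output without the restriction: "The number and percentage of patients with adverse events leading to permanent treatment discontinuation will be summarized by primary SOC" and the lower MedDRA levels.

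Two other places matter. Exclusion criterion E03 in protocol 7.3 bars "Any patient who experienced an adverse event leading to permanent discontinuation from a prior study". SAP 2.2, like protocol 13.3, tabulates treatment discontinuation by reason, and that table is not limited to treatment-emergent events.

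**The concern.** The primary endpoint of this study is the incidence of adverse events, and the proportion who stop because of one is a standard tolerability summary. Every patient enters from another trial, so ongoing events at entry are expected; the AE switch pages and the dedicated listing show that the sponsor expects some of them to end treatment here.

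For such an event, if it has not worsened or become serious, neither study produces a tabulated AE discontinuation. The parent study could not count it, because the patient had not stopped there. The extension does not count it, because onset came before the first LTS11210 dose. Leaving it out can only lower the AE-discontinuation percentage. The protocol text does not announce the restriction, and SAP 1.5 and 1.6, which record statistical changes, do not mention it.

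**Working it through.** The plan gives no figure that depends on this rule, so there is none to reproduce. The check is a trace of the definitions, followed by a scale calculation.

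**1. Where each kind of event goes when it leads to permanent discontinuation in LTS11210**

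| Event | Class under SAP 2.1.3.1 | Overview line and discontinuation tables | Carried-over listing | Disposition by main reason |
|---|---|---|---|---|
| Starts after the first LTS11210 dose | TEAE | Yes | No | Yes, if the main reason |
| Starts in the parent study, ongoing, then worsens or becomes serious | TEAE | Yes by definition, though not said outright | Also fits its wording | Yes, if the main reason |
| Starts in the parent study, ongoing, unchanged | Pre-treatment | No | Yes | Yes, if the main reason |

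Only the third row is left out of the AE tables. The second row is settled by the TEAE definition, but the text is not tidy. The parallel listing for carried-over serious events is expressly confined to non-treatment-emergent ones, whereas the discontinuation listing has no such qualifier.

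**2. Protocol against SAP**

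In protocol 13.5.4.1 the paragraphs on deaths and on AESIs carry a treatment-emergent limit. The paragraph on discontinuation does not, and neither does the one on serious events. The SAP applies the limit to discontinuations. The changes listed in SAP 1.5 by amendment do not include this, and SAP 1.6 only refers back to 1.5.

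**3. Scale**

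Inputs are the roll-over counts in the SAP:

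- SAP 1.3: 243 + 1040 + 7 + 168 + 454 + 111 = 2023.
- SAP 1.1: 1283 + 7 + 456 + 168 + 111 = 2025.
- Monotherapy (EFC13752): 111 in both.
- Sarilumab + DMARD: 2023 − 111 = 1912, or 2025 − 111 = 1914.

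The AE tables use the safety population. I take the roll-over counts as an approximation to it. The two groups are reported separately, so each has its own denominator.

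If k patients are omitted from a group of N, the percentage falls by 100 × k / N points:

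| k (assumed) | Sarilumab + DMARD, N = 1912 | Monotherapy, N = 111 |
|---|---|---|
| 1 | 100 × 1 / 1912 = 0.05 | 100 × 1 / 111 = 0.90 |
| 5 | 100 × 5 / 1912 = 0.26 | 100 × 5 / 111 = 4.50 |
| 10 | 100 × 10 / 1912 = 0.52 | 100 × 10 / 111 = 9.01 |

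Using 1914 in place of 1912 leaves the first two DMARD results unchanged to two decimals, apart from rounding in the third. The values of k are illustrative; the documents give no count. Results are also shown by previous treatment, where each column is smaller and one patient weighs more, but the SAP does not give those column sizes.

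**The case against.** The case for leaving the plan alone has five parts.

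- **The patient is not lost.** A reader might infer that such a patient is in no discontinuation rate at all. That is not so: disposition by main reason gives a number and a percentage of enrolled patients, with time to discontinuation. This stands. That table has no SOC/PT breakdown and no exposure-adjusted rate, uses enrolled rather than treated patients, and records only the main reason. It does not supply what protocol 13.5.4.1 describes.
- **The affected set is narrow.** A reader might infer that every parent-study event is excluded. It is not: one that worsens or becomes serious is a TEAE. Criteria E11, E13 and E14 also screen out patients with events judged to affect safety or participation, interruptions beyond 31 days, and those already meeting permanent-discontinuation criteria. A patient who enters below a laboratory stopping threshold and later crosses it will generally have worsened. This stands and keeps the number down.
- **The protocol conflict is mild.** A reader might infer that the protocol promises to count all adverse events. It does not say so, and section 13.2.2 applies one observation period, starting at the first LTS11210 dose, to all safety observations. The SAP's reading is defensible. What remains is that the protocol paragraph states no limit, the SAP adds one, and the step is not recorded.
- **Nothing is concealed.** The listing identifies each case. True, but a listing gives no percentage.
- **Pre-entry events do not belong in treatment-emergent rates.** Exposure is counted from the first LTS11210 dose, and some patients came from placebo or tocilizumab, so a carried-over event need not have begun on sarilumab. This is a sound reason not to merge them into the TEAE tables, and the fix below does not.

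**Conclusion.** The point holds in a limited form. An adverse event ongoing from a parent study that neither worsens nor becomes serious, and then leads to permanent discontinuation in LTS11210, is in no AE-discontinuation table of either study. It has a listing entry, and the patient counts in disposition if the event is the main reason. The rule can only lower the AE-discontinuation figure.

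The size is unknown and probably small: about 0.05 percentage points per omitted patient in the sarilumab + DMARD group and 0.90 points in the monotherapy group, taking the roll-over counts as denominators. One or two cases would be invisible in the larger group but noticeable among 111 patients.

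A reader might go further and infer that the loss falls mainly on patients already taking sarilumab at entry, or mainly in the first months. The documents give no data on either, so neither is claimed.

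A secondary point is the undefined overlap: the SAP should say whether a worsened carried-over event is tabulated, listed or both.

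**What to change.** Keep the TEAE tables, their exposure-adjusted rates and the listing as they are. Add to SAP 2.4.4.1:

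1. One summary giving the number and percentage of patients with any adverse event leading to permanent discontinuation in LTS11210, by SOC and PT, in two parts: treatment-emergent (including carried-over events that worsened or became serious) and carried-over unchanged.
2. A sentence stating that carried-over events that worsened or became serious belong in the TEAE discontinuation table, and whether they also stay in the listing.
3. A reconciliation of the total with the disposition table, explaining differences due to denominator (enrolled against treated) and criterion (main reason against any event).
4. An entry in SAP 1.6 recording that the main tables apply a treatment-emergent limit that protocol 13.5.4.1 does not state.

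The SAP suppresses the four-level TEAE table for small numbers ("The table summary will be presented only if the number of patients concerned is greater than 3"). The added summary should be shown whatever the count, since the carried-over part may be that small.

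The cost is a few lines of SAP text and one extra summary from data already extracted for the listing. The combined figure will be slightly less favourable than the TEAE figure if any such cases exist.
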